5.2.1.2 Dose Escalation of Investigational Product

MK-8521 or MK-8521 Placebo Treatment Groups

Subjects randomized to MK-8521 or MK-8521 placebo will begin the trial (**Visit 3/Day 1**) on 0.1 mL from each vial (60 µg/day for subjects randomized to active MK-8521).

At **Visit 4/Day 7**, the dose should be increased to 0.2 mL from each vial (120 μ g/day for subjects randomized to active MK-8521).

At Visit 5/Day 14, the dose should be increased to 0.3 mL from each vial (180 μg/day for subjects randomized to active MK-8521).

At **Visit 6/Day 21**, the dose from the MK-8521 300 μ g vial (labelled Vial D) should be increased to 0.5 mL/day (300 μ g/day for subjects randomized to the MK-8521 300 μ g treatment group).

Note the following related to the dose escalation:

- The dose escalation regimen for MK-8521 may be modified by the investigator to appropriately manage observed GI intolerance. Specifically, the investigator may decide to delay one scheduled dose increase for up to 7 days based upon tolerability (e.g., GI adverse events).
- The dose from both vials of MK-8521 or MK-8521 placebo must reach 0.3 mL/day (180 μ g/day for subjects randomized to active MK-8521) by Day 21.
- The dose from Vial D should reach 0.5 mL/day (300 µg/day for subjects randomized to the MK-8521 300 µg treatment group) by Day 28.
- Subjects who cannot tolerate 0.5 mL/day from Vial D may continue in the trial on 0.3 mL/day (180 μ g/day for subjects randomized to active MK-8521) from each vial.
- No dose changes are allowed beyond Day 28.
- See Table 6 for guidance on dose escalation.
- •An asymptomatic increase in HR that does not meet discontinuation criteria (Section 5.9) should not delay dose escalation.

The rationale for this dose escalation regimen can be found in Section 4.2.2.1.

Protocol/Amendment No.: 004-02

Table 6 Dose Escalation for Subjects Randomized to MK-8521 or Placebo

Vial	Visit 3/ Day 1	Visit 4/ Day 7	Visit 5/ Day 14	Visit 6/ Day 21	Visit 7/ Day 28
MK-8521 180 μg or matching placebo ¹ Vial C	initiate 0.1 mL/day	increase to 0.2 mL/day	increase to 0.3 mL/day ³	continue 0.3 mL/day ³	continue 0.3 mL/day ³
MK-8521 300 μg or matching placebo ¹ Vial D	initiate 0.1 mL/day	increase to 0.2 mL/day	increase to 0.3 mL/day ³	increase to 0.5 mL/day ^{2,3}	If any step is delayed, the final dose of 0.5 mL/day must be reached at Visit 7/Day 28 ^{2,3}

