8.2.4 Analysis Populations

8.2.4.1 Efficacy Analysis Populations

The Full Analysis Set (FAS) population will serve as the primary population for the analysis of efficacy data in this study. The FAS population includes subjects who take at least one dose of study therapy and have at least one efficacy measurement either at baseline or during the treatment period. Subjects will be included in the treatment group to which they were randomized.

A secondary population for analyzing primary and key secondary efficacy endpoints at Week 12 will be the Per-Protocol (PP) population. All randomized subjects who take at least one dose of study medication, with a measurement at baseline and the time point of interest (Week 12), without the protocol deviations described below will be included in this population.

Protocol deviations used to determine the PP population are not just a repetition of the exclusion and inclusion criteria in the protocol, but a clinical assessment of deviations from the protocol-specified criteria that will either affect or confound the measures of efficacy. The following rules define protocol violators during the trial period of interest (Day 1 through Week 12) and will be used to identify such subjects prior to unblinding. Subjects with any of the following violations will be excluded from the PP population at all time points.

- **Drug compliance:** A subject will be excluded from the PP population due to low compliance if either of the following applies:
 - Compliance assessed by prime therapy records provided by the investigator in the eCRF is <90%.
 - <75% of evaluable trough PK samples have quantifiable concentrations. This
 criterion is applicable only to subjects in the MK-8521 and liraglutide groups.
 

Protocol/Amendment No.: 004-02

Additionally, a site will be deemed to have low compliance and all subjects from that site (including those randomized to the placebo group) will be excluded from the PP population if either of the following applies:

- o For sites with exactly 2 subjects randomized to active groups, both of these subjects have low compliance based on trough PK criterion noted above.
- o For sites with 3 or more subjects randomized to active groups, ≥50% of subjects have low compliance based on the trough PK criterion noted above.
- Use of prohibited medications: The list of prohibited medications can be found in Section 5.5.

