 - o If a subject takes any prohibited antihyperglycemic medications after randomization (Visit 3/Day 1) for a total of ≥14 days or ≥7 consecutive days, he/she will be identified as a protocol violator.
 - o A subject with pharmacologic doses of corticosteroid use ≥ 2 consecutive weeks after randomization will be identified as a protocol violator.
- Incorrect double-blind study medications: If a subject receives incorrect double-blind study medication for a total of ≥14 days during the trial period of interest, then he/she will be identified as a protocol violator.
- Subjects who cannot tolerate 0.5 mL/day from Vial D: If a subject does not tolerate the full target dose of 0.5 mL/day MK-8521 from Vial D, he/she will be identified as a protocol violator. This criterion will only be applied to subjects randomized to the MK-8521 300 µg group.

The final determination on protocol deviations, and thereby the composition of the PP population, will be made prior to the final unblinding of the database and will be documented.

An additional secondary population to analyze the efficacy endpoints will be the modified FAS (mFAS). The modified FAS population is a subset of FAS population that excludes sites identified as having low compliance (as described in the drug compliance description for the PP population above).

The number of subjects included in the FAS, PP and mFAS populations may vary across endpoints due to the degree of missing data for each endpoint. Any substantial differences between conclusions based on the FAS, PP population, and mFAS population will be investigated.

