
Protocol/Amendment No.: 004-02

In the event that fewer than 75% of the subjects in the 300 μ g dose group receive the full target dose, suggestive of dose-intolerance, the hypothesis test MK-8521 180 μ g vs. placebo will be performed first. In this case if the 180 μ g dose vs. placebo is statistically significant, the primary hypothesis (for A1C) will be considered met and then the 300 μ g dose will be tested.

If success is achieved in the test of the primary hypothesis (i.e., at least one dose of MK-8521 provides significantly greater reduction in A1C relative to placebo following the testing procedure described above), then each of the MK-8521 doses will be compared to liraglutide using the same ordered testing procedure above. Continuous efficacy endpoints such as FPG, body weight, LDL-cholesterol level, HDL-cholesterol level, triglyceride level, systolic blood pressure (SBP), and diastolic blood pressure (DBP) will be analyzed using the above cLDA method described for A1C. Change and percent change from baseline in triglycerides will be analyzed using multiple imputation (MI) of missing values (if any) in conjunction with a robust regression (RREG) approach that uses M-estimation. Because the percent change in triglycerides typically has a skewed distribution, the cLDA model which is based on the symmetric normal distribution is not appropriate.

The primary (A1C) and key secondary endpoints (FPG and body weight) will also be analyzed in the PP population using an ANCOVA model. The ANCOVA model will include treatment, stratification factors of A1C (<8.5%, $\ge8.5\%$), BMI (<30 kg/m², ≥30 kg/m²) and AHA washout status (Yes, No), and baseline value. By definition, there will be no missing outcome data in the PP population.

Key efficacy endpoints will also be analyzed in the mFAS population using the same statistical methods stated for the FAS population.

Table 12 summarizes the analysis strategy for all efficacy endpoints. The strategy to address multiplicity issues with regard to multiple treatment comparisons and multiple endpoints is described in Section 8.2.6, Multiplicity.

Table 12 Analysis Strategy for Efficacy Endpoints

Endpoint (All at Week 12)	Approach	Statistical Method	Analysis Population	Missing Data Approach
Primary				
Change from baseline in A1C	P	cLDA	FAS	Model-based
Change from basefine in ATC	S	ANCOVA	PP	NA
	S	cLDA	mFAS	Model-based
Key Secondary				
Change from baseline in FPG	P	cLDA	FAS	Model-based
	S	ANCOVA	PP	NA

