	S	cLDA	mFAS	Model-based
Change from baseline in body weight	P	cLDA	FAS	Model-based
	S	ANCOVA	PP	NA
	S	cLDA	mFAS	Model-based
Other Endpoints				
Change and percent change from baseline in LDL and				
HDL	P	cLDA	FAS	Model-based
Change from baseline in SBP and DBP				
Change and percent change from baseline in	P	Robust	FAS	Multiple
triglycerides	Р	Regression	FAS	Imputation
P=Primary; S=Secondary				

Protocol/Amendment No.: 004-02

The following exploratory efficacy analyses may be performed. Analysis methods will be described in a separate document, as appropriate.

- Insulin secretion (HOMA-β) and insulin resistance (HOMA-IR). A decision for the analysis will be based on potential for utility in light of emerging clinical efficacy and safety outcomes.
- Glucagon receptor activation biomarkers (including ketones, glucagon, FGF-21 and kisspeptin). Analyses may be performed if the primary hypothesis is met or if the results are considered important for future dual peptide programs.
- If fewer than 75% of the subjects in the 300 μg dose group receive the full target dose, an additional analysis with pooling of subjects on 180 μg dose may be performed. Those subjects not tolerating the 300 μg dose and continuing on the 180 μg dose will be pooled with the subjects in the 180 μg dose group.
- The relationship between genetic variation and response to the treatments administered, and variation across the human genome with clinical data collected in this study may be analyzed. A decision for the analysis will be based on potential for utility in light of emerging clinical efficacy and safety outcomes.

Due to the limited duration of analyte stability in collected PK samples, it is necessary to conduct PK sample analysis on a rolling basis while the study is ongoing. Early unblinding limited to staff critical for the conduct of PK sample analyses will occur to allow PK analysis of subjects who received the drug (MK-8521) being measured. No multiplicity adjustment is being made since the conduct of the study is not dependent on the unblinding for early PK analysis. Unblinded PK data or results will not be shared with the protocol team prior to study completion and database lock.

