8.2.6 Multiplicity

The Type-I error rate over the multiple treatment comparisons (i.e., two MK-8521 doses versus placebo) for the primary hypothesis will be controlled by an ordered testing procedure. This testing procedure will first test the 300 μ g dose. If a statistically significant result is observed, then the 180 μ g dose will be tested and the primary hypothesis test will be considered successful, regardless of the outcome of the 180 μ g vs. placebo.

In the event that fewer than 75% of the subjects in the 300 μ g dose group receive the full target dose, the first test of MK-8521 vs. placebo will be performed at the 180 μ g dose. If the 180 μ g dose vs. placebo is statistically significant, then the primary hypothesis will be considered successful.

The secondary hypotheses for body weight and FPG are deemed supportive and will only be tested if significance is achieved at the corresponding dose level for A1C.

Comparisons involving other efficacy endpoints and other treatment comparisons (MK-8521 doses vs. liraglutide) are considered supportive or exploratory and will be made at α =0.05

Protocol/Amendment No.: 004-02

nominal level (two-sided) and 95% CIs will be provided. No multiplicity adjustment will be performed for these other comparisons.

From a safety standpoint, application of a multiplicity adjustment could potentially mask a safety concern. No multiplicity adjustment is planned for safety endpoints.

An interim analysis will be performed to assist in program planning, support sample size reestimation, and support assessment of whether the study should be terminated based on an assessment of the overall data and in consideration of programmatic goals (described in Section 8.2.9). This is not a pivotal trial and the trial will not be stopped early for positive results. Therefore, no alpha adjustment will be made for this interim analysis.

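### Does the 75% rule that sets the dose test order need a fuller definition of who has received the full target dose?

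*Combined protocol and SAP*

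**What the plan says.** Section 8.2.5.1 sets a fixed order for the primary A1C comparisons: 300 µg against placebo, then 180 µg if the first is significant. The order reverses when fewer than 75% of subjects in the 300 µg "dose group receive the full target dose, suggestive of dose-intolerance". Section 8.2.6 repeats this: if fewer than 75% of the 300 µg "dose group receive the full target dose, the first test of MK-8521 vs. placebo will be performed at the 180" µg dose. The same threshold opens an optional exploratory analysis in 8.2.5.1: if fewer than 75% of the 300 µg "dose group receive the full target dose, an additional analysis with pooling of subjects on 180" µg may be run. That bullet describes the people to be pooled as "Those subjects not tolerating the 300" µg dose and continuing on 180 µg.

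Three other places bear on the count.

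- Section 8.2.4.1 keeps Full Analysis Set (FAS) subjects in their randomized group. It also makes a 300 µg subject a per-protocol violator "If a subject does not tolerate the full target dose of 0.5 mL/day MK-8521 from Vial D", and the decision on deviations "will be made prior to the final unblinding of the database and will be documented".
- Section 5.2.1.2 has Vial D reach 0.5 mL/day by Day 28, lets subjects who cannot tolerate it continue on 0.3 mL/day, and adds: "No dose changes are allowed beyond Day 28".
- Section 8.2.7 assumes cumulative attrition of 8% at Week 6 and 16% at Week 12.

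**The concern.** The rule picks the first test, and the first test decides whether the primary hypothesis is met. By default only 300 µg can meet it; after the switch only 180 µg can. Yet the rule does not say whether the denominator is all randomized, all treated or FAS subjects, by which day the dose must have been received, or how to count someone who leaves during escalation. The per-protocol set cannot stand in as the denominator. It requires subjects "with a measurement at baseline and the time point of interest (Week 12), without the protocol deviations described below", so it has already lost the non-tolerators and anyone without a Week 12 value.

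Placebo and 180 µg subjects go through the same Vial D escalation, so the percentage in the 300 µg arm can be computed only with treatment codes. If the counting were settled after results were known, the order could be chosen to suit them. Section 3.1 adds to the unease: it words the hypothesis as 300 µg or both doses, which does not describe success on 180 µg alone.

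**Working it through.** **1. The plan's own figure.** Inputs from 8.2.7: difference 0.8%, conditional SD 1.1%, effective n 35 per arm, two-sided 0.05.

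- SE = 1.1 × √(2/35) = 0.263; 0.8/0.263 = 3.04.
- Power = 86.0% (normal) or 85.1% (noncentral t, 68 df), against about 85% stated.
- Half-width = 1.96 × 0.263 = 0.515 (normal) or 0.525 (t), against 0.52% stated.

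None of this depends on the 75% rule.

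**2. What the text settles.**

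- Denominator: subjects in the 300 µg dose group, in a procedure run on the FAS by randomized group.
- Cut-off: Day 28, after which the dose cannot change.
- Step-downs to 0.3 mL: not on the full target dose. The reference to dose-intolerance in the rule and the pooling bullet both point this way.
- Dropouts before a first 0.5 mL dose: on the plain meaning of receive, they have not received it.

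Only the last item leaves room for argument, and only for subjects who left for a reason other than intolerance.

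**3. A case where it matters.** Of 40 subjects, 3 leave early for other reasons and 8 step down, so 29 receive 0.5 mL. Then 29/40 = 72.5% switches the order; leaving the dropouts out, 29/37 = 78.4% does not.

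**4. How often the two counts disagree.** Let D ~ Bin(40, d) be early dropouts for other reasons and K ~ Bin(40 − D, q) the intolerant. The order switches if

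- count A (dropouts not receiving): 40 − D − K < 30;
- count B (dropouts left out): 40 − D − K < 0.75 × (40 − D).

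Both d and q are assumptions. Spreading the 8% evenly over 42 days gives 8% × 21/42 = 4% by Day 21. That is all-cause attrition, so 4% is high for non-intolerance dropout alone; 2% takes half of it. Exact binomial results:

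| q | d | A switches | B switches | A and B differ |
|---|---|---|---|---|
| 10% | 2% | 0.5% | 0.3% | 0.3% |
| 10% | 4% | 1.5% | 0.3% | 1.2% |
| 20% | 2% | 23.2% | 19.9% | 3.3% |
| 20% | 4% | 31.5% | 20.8% | 10.7% |
| 30% | 2% | 75.5% | 73.1% | 2.4% |
| 30% | 4% | 81.0% | 73.6% | 7.4% |

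A third count, treating people who never took 0.5 mL as having received it, contradicts the wording. Including it would raise the 10.7% to 18.4%.

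**5. Effect on the primary conclusion.** With a true 0.8% at both doses and a shared placebo arm (correlation 0.5), each dose is significant with probability 0.860 and at least one with probability 0.948. Exactly one is significant in 2 × (0.948 − 0.860) ≈ 17.5% of trials, and only there does the order matter. If dosing status is independent of the A1C tests, the count alters the verdict in at most 0.107 × 0.175 = 1.9% of trials in the table. If 180 µg has half the effect, exactly one dose is significant in 55.4%, and the product is 0.107 × 0.554 = 5.9%.

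**6. Type I error.** A fixed order gives 5.0%. Always choosing the better of two orders after seeing results gives 9.1%. If that choice existed only when counts A and B differ, and were abused every time, the error would be 0.05 + 0.0407 × P(differ): 5.0–5.1% at d = 2% and 5.0–5.4% at d = 4%.

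**The case for a change.** The strongest case for a change is that a rule governing the primary test should leave nothing to the analyst, and that one sentence would close the gap. The wording does vary between receiving and tolerating, and the commitment to settle matters before unblinding is written for the per-protocol set, not for this rule. Taking all 8% of Week 6 attrition as non-intolerance dropout before the full dose, and admitting all three counts, the order would differ in 7%, 39% and 33% of trials at 10%, 20% and 30% intolerance.

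The missing sentence is a fact. The large figures do not carry over: they use all-cause attrition to Day 42 for a narrower cause and a shorter period, and they include a count the text rules out. Intolerance of 20% to 30% is also an assumption. Sections 4.1.2.2 and 4.2.2 report generally good tolerability up to 300 µg in P003 and no gastrointestinal discontinuations on MK-8521, though in a small and short study.

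The worry about late choice is weakened by what the plan already requires. Per-protocol violators are identified before unblinding, so inability to take 0.5 mL from Vial D has to be judged from dosing records for subjects whose arm is still masked. That work supplies most of what the 75% rule needs. The remaining dropouts can be documented then too.

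The mismatch with section 3.1 is one of wording. Sections 8.2.5.1 and 8.2.6 state when the hypothesis is met, including on 180 µg after a switch, and those are the sections the analysis follows.

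**Conclusion.** No change is needed. The rule lacks a counting sentence, but its words, the FAS convention and the Day 28 limit fix nearly all of the count. The open category is people in the 300 µg arm who leave before a first 0.5 mL dose for a reason other than intolerance. At 2% to 4% of 40 that is about one person (0.8 to 1.6 expected).

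On the two plausible counts the order differs in 0.3–1.2%, 3.3–10.7% and 2.4–7.4% of trials at 10%, 20% and 30% intolerance. The dropout and intolerance rates are assumptions; the documents give only the 8% and 16% attrition figures. Any count fixed from dosing data without sight of the efficacy results keeps type I error at 5%. Power, sample size and interval widths do not move, and with equal effects the chance of meeting the primary hypothesis is about 86% in either order. The interim futility criteria must be met for both doses, and the sample size review uses only the conditional SD, so neither depends on the order.

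A team recording per-protocol decisions before unblinding would naturally record this count as well. In a trial the plan calls not pivotal, that is routine analyst judgement.

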8.2.5.2 Safety Analyses

The ASaT population and modified ASaT population will be employed for safety analyses. Safety and tolerability will be assessed following a tiered approach by clinical review of all relevant parameters including AEs, predefined limits of change (PDLC), laboratory tests, and vital signs. For all comparisons described below, each of the two doses of MK-8521 will be compared versus placebo and versus liraglutide.

The analysis of safety parameters will follow a tiered approach. The tiers differ with respect to the analyses that will be performed. Safety parameters or adverse events of interest that are identified *a priori* constitute "Tier 1" safety endpoints that will be subject to inferential testing for statistical significance with p-values and 95% CIs provided for between-group comparisons using the Miettinen and Nurminen method [23], an unconditional, asymptotic method. Other safety parameters will be considered Tier 2 or Tier 3. Tier 2 parameters will be assessed via point estimates with 95% CI provided for between-group comparisons; only point estimates by treatment group are provided for Tier 3 safety parameters.

Membership in Tier 2 requires that at least 4 subjects in any treatment group exhibit the event or meet PDLC criterion; all other AEs and PDLCs will belong to Tier 3.

The threshold of at least 4 events was chosen because the 95% CI for the between-group difference in percent incidence will always include zero when treatment groups of equal size

Protocol/Amendment No.: 004-02

each have less than 4 events and thus would add little to the interpretation of potentially meaningful differences. Because many 95% CIs may be provided without adjustment for multiplicity, the CIs should be regarded as a helpful measure to be used as a flagging method—to identify events of potential clinical relevance, that require additional review—and not a formal method for assessing the statistical significance of the between-group differences in AEs and PDLCs.

Table 13 summarizes the analysis strategy for safety endpoints. In addition, as some of the subjects in the MK-8521 300 μ g and liraglutide arms may not get to the full target dose, sensitivity analyses including only subjects with the full dose may be performed for Tier 1 safety parameters.

Table 13 Analysis Strategy for Safety Endpoints

Tier	Safety Endpoint	p-Value	95% CI for Treatment Comparisons	Descriptive Statistics
Tier 1	AE of symptomatic hypoglycemia	X	X	X
Tier 2 ¹	Change from baseline in HR		X	X
	HR >100 bpm or HR increase >30 bpm		X	X
	AE summary measures		X	X
	Specific AEs ² , SOCs, specific confirmed CV SAEs, and PDLCs		X	X
Tier 3	All endpoints listed under Tier 2 (above) that have incidence <4 subjects in all treatment groups			X
	Additional hypoglycemia adverse event endpoints			X
	Change from baseline results (laboratory measurements, ECG, and vital signs)			X

¹ Non-continuous endpoints listed here will qualify for Tier 2 only if the incidence is ≥4 subjects in at least one of the treatment groups.

Analysis of Hypoglycemia

The Tier 1 analysis for hypoglycemia will include the numbers and percentages of subjects experiencing one or more adverse events of symptomatic hypoglycemia, regardless of glucose value.

The Tier 2 analysis for hypoglycemia will include the numbers and percentages of subjects experiencing one or more of each the following:

- Adverse events of hypoglycemia (symptomatic or asymptomatic), regardless of biochemical documentation.
- Adverse events of documented hypoglycemia, defined as adverse events of symptomatic hypoglycemia with a concurrent glucose measurement of <70 mg/dL (<3.9 mmol/L)

² Among those endpoints not pre-specified as Tier 1 endpoints.

AE=Adverse Event; CI=Confidence Interval; ECG=Electrocardiogram; PDLC=Pre-Defined Limit of Change;

SAE=Serious adverse event; SOC=System Organ Class; X = results will be provided.

Product: MK-8521

Protocol/Amendment No.: 004-02

 Adverse events of severe hypoglycemia, defined as adverse events of symptomatic hypoglycemia that required assistance, either medical or non-medical, regardless of whether such assistance was obtained, and regardless of biochemical documentation. These events will be further sub-classified as:

- Those that required medical assistance. Adverse events of symptomatic hypoglycemia that included a markedly depressed level of consciousness, loss of consciousness, or seizure will be classified as having required medical assistance, whether or not medical assistance was obtained
- Those that did not require medical assistance (i.e., those episodes that required non-medical assistance to treat).

The Tier 3 summary of hypoglycemia will include the following, based on episodes classified by the investigator as adverse events:

- The numbers and percentages of subjects with each of the following, overall and by lowest reported glucose category (<50 mg/dL [<2.8 mmol/L], ≤70 mg/dL [≤3.9 mmol/L], >70 mg/dL [>3.9 mmol/L], or unknown). A subject's lowest glucose category will be classified as unknown only if no glucose measurements are available for that subject.
 - 1. any episodes (symptomatic or asymptomatic)
 - 2. symptomatic episodes
 - 3. asymptomatic episodes
- The numbers and percentages of subjects with episodes having precipitating factors
- The number of episodes per subject
- The number of each of the following (summed across all subjects). The overall summary will include an indication of whether precipitating factors were present.
 - 1. all episodes (symptomatic or asymptomatic)
 - 2. symptomatic episodes
 - 3. asymptomatic episodes

Categorization of episodes by glucose level will be performed based on the units (mg/dL or mmol/L) in which the glucose measurements were reported.

A summary of subjects with episodes that were reported on the hypoglycemia assessment (HA) eCRF but were not classified by the investigator as adverse events will also be provided. If a substantial number of subjects had episodes that were not classified as adverse events, then additional summaries may be provided for the Tier 3 endpoints above, including all episodes reported on the HA eCRF (i.e., not restricted to adverse events). It is expected that all symptomatic hypoglycemia episodes will be classified by the investigator as adverse events and, thus, that any episodes that are not classified as adverse events will be asymptomatic episodes.

Protocol/Amendment No.: 004-02

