5.3 Randomization or Treatment Allocation

Randomization will occur centrally using an interactive voice response system / integrated web response system (IVRS/IWRS). There are 4 treatment arms. Subjects will be assigned randomly in a 1:1:1:1 ratio to MK-8521 300 μ g, MK-8521 180 μ g, MK-8521 matching placebo, or open-label liraglutide, respectively.

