8.2.3.2 Safety Endpoints

Safety and tolerability will be assessed by a clinical review of all relevant adverse experiences and monitoring variables related to blood chemistry, hematology, vital signs, and ECG.

Tier 1 safety endpoints are adverse events of symptomatic hypoglycemia (see Table 13).

Tier 2 safety endpoints include changes from baseline in HR at different time points.

Adverse events (overall summary, specific AEs, and AEs by system organ class) and PDLCs in laboratory and vital signs parameters (including proportion of subjects with HR>100 bpm or HR increase > 30 bpm) will be classified as belonging to "Tier 2" or "Tier 3", based on the number of events observed.

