8.2.7 Sample Size and Power Calculations

After 12 weeks of MK-8521, a reduction of $\geq 0.8\%$ in A1C and ≥ 2 kg in body weight, relative to placebo, is expected.

A total of approximately 160 subjects will be randomized in a 1:1:1:1 ratio to 300 µg dose and 180 µg dose of MK-8521, placebo or liraglutide. A sample size of 40 subjects per arm will provide approximately 85% power to detect a treatment difference of 0.8% in A1C reduction at Week 12 (alpha=0.05, two-sided test). The half-width of the 95% CI of A1C is 0.52%. This calculation is based upon the following assumptions:

- 1. Cumulative attrition rates at Weeks 6 and 12 are 0.08 and 0.16, respectively.
- 2. The conditional standard deviation is 1.1%.
- 3. The conditional correlation between Weeks 6 and 12 is 0.76732.

The correlation between Weeks 6 and 12 is derived based on data from MK-0431 PN020. The high attrition rates are used to account for dropout risks due to the requirement of taking 2 subcutaneous injections daily and any potential AEs in this first outpatient trial of MK-8521. The SD is assumed to be 1.1% to account for more variability in patients with higher baseline A1C. The sample size of 40 subjects will be equivalent to an effective sample size of 35 subjects at Week 12, which accounts for information loss due to missing data and correlation among repeated measures and is derived using the method proposed by Lu, et al. [24].

The sample size of 40 subjects per arm will provide approximately 87% power to detect a treatment difference of 2 kg in body weight loss at Week 12. The half-width of the 95% CI of body weight is 1.23 kg. This calculation is based on the same dropout rates and correlation for the A1C and on the conditional standard deviation of 2.7 kg.

The sample size of 40 subjects per arm will provide approximately 88% power to detect a treatment difference of 30 mg/dL in FPG at Week 12. The half-width of the 95% CI of FPG is 18.9 mg/dL. This calculation is based on the same dropout rates and correlation for the A1C and on the conditional standard deviation of 40 mg/dL.

Protocol/Amendment No.: 004-02

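### The four-subject rule removes the 95% CI for the heart-rate threshold endpoint when events are few, although the interval's upper limit is then still informative

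*Combined protocol and SAP*

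**What the plan says.** Section 8.2.5.2 sets three tiers. Tier 1 gets p-values and CIs, Tier 2 gets point estimates and CIs, and Tier 3 gets point estimates by arm only. Entry to Tier 2 depends on the observed count: "Membership in Tier 2 requires that at least 4 subjects in any treatment group exhibit the event or meet PDLC criterion". The justification is that "the 95% CI for the between-group difference in percent incidence will always include zero when treatment groups of equal size" each have fewer than four events, from which the plan concludes that the interval would contribute little.

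Table 13 lists heart rate above 100 bpm or a rise of more than 30 bpm as a Tier 2 endpoint with a 95% CI. Its footnote then makes that conditional: "Non-continuous endpoints listed here will qualify for Tier 2 only if the incidence is" at least four subjects in one or more arms. The Tier 3 row takes the listed endpoints that fall short in every arm. Section 8.2.3.2 confirms that the heart-rate event is handled this way: limits-of-change endpoints, "including proportion of subjects with HR>100 bpm or HR increase > 30 bpm) will be classified as belonging to 'Tier 2' or 'Tier 3" according to the number of events seen. No other section restores an interval for an endpoint moved to Tier 3.

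Section 8.2.5.2 describes the unadjusted CIs as an aid to flagging events for further review and not as formal tests.

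**The concern.** That an interval includes zero is a statement about its lower limit. With few events, the useful end is the upper limit, which shows how large an excess the data have not excluded. The rule drops the interval because of the first property and so loses the second.

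This matters most for heart rate. Safety and tolerability is primary objective 2 (Section 3.1). Section 4.1.2.2 names heart-rate increase as one of two potential safety issues seen so far, and Section 4.2.2 gives a placebo-adjusted mean rise of about 8.3 bpm over 24 hours at 300 µg. Section 4.2.3.2 counts heart-rate threshold events among the key heart-rate endpoints, though it words them as sustained or symptomatic events. Under the rule, 3 of 40 on MK-8521 against 0 of 40 on placebo would appear as 7.5% against 0%, with nothing to show how imprecise that contrast is.

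**Working it through.** **Inputs**
- 40 subjects per arm. Section 8.2.7: "A sample size of 40 subjects per arm will provide approximately 85% power".
- Equal arms. Section 5.3: "Subjects will be assigned randomly in a 1:1:1:1 ratio".
- No reduction for dropout. Section 8.2.7 assumes attrition ("Cumulative attrition rates at Weeks 6 and 12 are 0.08 and 0.16, respectively"), but the safety population in Section 8.2.4.2 needs only one dose.
- Method. Section 8.2.5.2 specifies, for Tier 1, "95% CIs provided for between-group comparisons using the Miettinen and Nurminen method [23], an unconditional, asymptotic method". It names no method for Tier 2 proportions; I assume the same one.

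**Formula.** For a difference Δ, with p̃₁ and p̃₂ the maximum-likelihood estimates restricted to p̃₁ − p̃₂ = Δ and N = n₁ + n₂:

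z(Δ) = (p̂₁ − p̂₂ − Δ) / √{ [p̃₁(1−p̃₁)/n₁ + p̃₂(1−p̃₂)/n₂] × N/(N−1) }

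The 95% limits are the values of Δ where z(Δ) = ±1.96.

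**Step 1: the plan's own threshold.** At Δ = 0 the restricted estimate is the pooled proportion.
- 3 vs 0: pooled 3/80 = 0.0375. Variance = 2 × 0.0375 × 0.9625/40 × 80/79 = 0.001828, and z = 0.075/0.04275 = 1.754. Below 1.96, so zero is inside the interval.
- 4 vs 0: pooled 4/80 = 0.05. Variance = 2 × 0.05 × 0.95/40 × 80/79 = 0.002405, and z = 0.100/0.04904 = 2.039. Above 1.96, so zero is excluded.

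All pairs with 0 to 3 events per arm include zero. The threshold of four is therefore reproduced for equal arms.

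**Step 2: the intervals that the rule withholds** (40 per arm, MK-8521 minus comparator, percentage points)

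| Events | 95% CI | Reported under the plan? |
|---|---|---|
| 0 vs 0 | −8.9 to +8.9 | No |
| 1 vs 0 | −6.5 to +13.0 | No |
| 2 vs 0 | −4.1 to +16.6 | No |
| 3 vs 0 | −1.7 to +20.0 | No |
| 3 vs 1 | −6.4 to +17.9 | No |
| 3 vs 3 | −13.6 to +13.6 | No |
| 4 vs 0 | +0.7 to +23.2 | Yes |

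The No rows assume that the other two arms also have fewer than four events. For scale only, Section 4.2.3.2 treats five heart-rate discontinuations as potentially more than 10% of one arm (5/40 = 12.5%). That is a different event, but 1, 2 or 3 vs 0 each leave an excess above 10 points open.

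**Step 3: sensitivity to arm size.** Section 8.2.9.2 allows up to 200 randomized, or 200/4 = 50 per arm. There the upper limits for 1, 2 and 3 vs 0 are 10.6, 13.5 and 16.3 points. At 35 per arm they are 14.7, 18.7 and 22.5.

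**Step 4: how often the rule would apply.** The documents give no event rates, so these are assumptions: 1% on placebo and one common rate in the three active arms. The chance that no arm reaches four events is P(X ≤ 3) for placebo times the cube of P(X ≤ 3) for an active arm, with X binomial(40, rate). At 5% this is 0.9993 × 0.8619³ = 0.64. Across active-arm rates:

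| Active-arm rate | No arm reaches 4 |
|---|---|
| 2.5% | 95% |
| 5% | 64% |
| 7.5% | 27% |
| 10% | 8% |

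**The case against.** The case for leaving the rule alone is reasonable. There is no safety hypothesis or margin. The CIs are declared to be a flagging aid, and safety is judged by clinical review. Even 0 vs 0 gives an upper limit of 8.9 points, so calling such intervals of little use is a defensible view in Phase IIa. Point estimates by arm are shown, so a reader with the arm sizes can derive the limit. Heart rate also has safeguards that do not depend on any CI: subjects meeting the discontinuation criteria are reported within 24 hours (Section 7.2.3.2), five such discontinuations on blinded product trigger unblinded review (Section 8.2.9.1), and heart-rate change is reviewed at the interim (Section 8.2.9.2). All of this stands and keeps the point small. It does not answer it: the safeguards govern trial conduct, and a derivable limit is still not a reported one.

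Four stronger readings are tempting, and the documents do not support them.
- **The safety objective as a whole loses its upper bound.** It does not. Mean change in heart rate is continuous and keeps its CI, and Tier 1 symptomatic hypoglycemia keeps its p-value and CI at any count.
- **The threshold causes real excesses to go unflagged.** With equal arms and fewer than four events in each, zero is always inside the interval, so reporting it adds no flag. Missed excesses reflect power at 40 per arm.
- **An unflagged event is taken as safe.** No section says so.
- **Severe hypoglycemia and confirmed cardiovascular SAEs need the same exemption.** Severe hypoglycemia is a subset of the Tier 1 event, and its tier is unclear: the hypoglycemia text places it in Tier 2, while Table 13 puts additional hypoglycemia endpoints in Tier 3. The cardiovascular SAEs are not defined, so an exemption could not be applied as written.

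**Conclusion.** The point holds as a narrow reporting gap. The plan's arithmetic is right, but its inference from a CI that includes zero to one that adds little is not. For the heart-rate threshold endpoint, the rule can withhold upper limits of 13.0, 16.6 or 20.0 points for 1, 2 or 3 events against none.

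These figures assume 40 per equal arm and the Miettinen-Nurminen method for Tier 2 proportions. How often the rule would apply depends on event rates that the documents do not give; over the assumed range it runs from 95% of trials to 8%. No test, error rate or conduct rule is wrong. This is a low-cost improvement, worth making because heart rate is a known signal under a primary safety objective.

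**What to change.** In Section 8.2.5.2, Table 13 (footnote 1 and the Tier 3 row) and the matching sentence of Section 8.2.3.2, exempt the endpoint of heart rate above 100 bpm or a rise of more than 30 bpm from the four-subject rule. State that its Miettinen-Nurminen 95% CI is reported whatever the count, for each MK-8521 dose versus placebo and versus liraglutide. Add that the interval describes the size of excess not ruled out and is not a pass/fail criterion, since the plan sets no safety margin. Keep the threshold for unplanned adverse event terms and laboratory limits of change.

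The cost is one sentence and 2 doses × 2 comparators = 4 intervals per safety population, or 8 over the two populations. Some will be wide. Sample size, alpha and trial conduct do not change.
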